## 9.3 Definitions of Disease Response

Definition of response in target lesions:

- **Complete Response (CR):** Disappearance of all target lesions
- **Partial Response (PR):** At least a 30% decrease in the sum of the diameters of target lesions, taking as reference the baseline sum diameters
- **Local Progressive Disease (LPD):** At least a 20% increase in the sum of the diameters of target lesions compared to baseline sum of target lesions, taking as reference the smallest sum on study (this includes the baseline sum if that is the smallest on study). The sum must also demonstrate an absolute increase of at least 5 mm in addition to the relative increase of 20%.
- **Distant Progressive Disease (DPD):** The appearance of at least 1 new lesion.
- **Stable Disease (SD):** Neither sufficient decrease to qualify as a PR or sufficient increase to qualify as PD, taking as reference the smallest sum diameters while on study.

Definition of response in non-target lesions:

- **Complete Response (CR):** Disappearance of all target lesions
- **Progressive Disease (PD):** Appearance of one or more new lesions and/or unequivocal progression of existing non-target lesions
- **Incomplete Response/Stable Disease (SD):** Persistence of one or more non-target lesions

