### 9.2 Definitions for disease assessment

- Measurable lesions: Lesions that can be accurately measured in at least one dimension with longest diameter at least 10 mm.
- Malignant lymph nodes: A lymph node will be considered measurable if it measures at least 15 mm in short axis.
- Non-measurable lesions: All other lesions <10 mm or lymph nodes <15 mm in short axis.
- Target lesions: Target lesions should be identified and measured at baseline. Target lesions include measurable lesions up to a maximum of two lesions per organ and up to five lesions in total that are representative of all involved organs. Target lesions should be selected on the basis of their size (lesions with the longest diameter) and are to undergo reproducible repeated measurements. If the largest lesion does not lend itself to reproducible measurement, it should not be considered a target lesion and instead the next largest lesion that can be measured reproducibly should be selected. A sum of the longest diameters for all target lesions will be calculated and reported as the baseline sum diameters. The baseline sum diameters will be used as reference to further characterize any objective tumor regression in the measurable dimension of the disease.
- Non-target lesions: All other lesions (or sites of disease) including any measurable lesions over and above the 5 target lesions should be identified as non-target lesions and should also be recorded at baseline. Measurements of these lesions are not required, but the presence, absence, or in rare cases unequivocal progression of each should be noted throughout follow-up.

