## 9.4 Evaluation of best overall response

Best overall response is the best response recorded from the start of radiation therapy until disease progression or recurrence, taking as reference for progressive disease the smallest measurements recorded since SABR.

Target Lesions	Non-Target Lesions	New Lesions	Overall Response
CR	CR	No	CR
CR	PR/SD	No	PR
PR	Non-PD	No	PR
SD	Non-PD	No	SD
PD	Any	Yes or No	PD
Any	PD	Yes or No	PD
Any	Any	Yes	PD

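### Two separate defects in the response rules: section 9.3 defines non-target complete response by the target lesions, and section 9.2 qualifies nodes on short axis but sums them on longest diameter

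*Combined protocol and SAP*

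**What the plan says.** **Non-target response.** Section 9.3 has a list headed "Definition of response in non-target lesions". Its CR entry reads "Disappearance of all target lesions", identical to the CR entry in the target list above it. SD in the same list is "Persistence of one or more non-target lesions", and progressive disease (PD) is "Appearance of one or more new lesions and/or unequivocal progression of existing non-target lesions". There is no PR category for non-target lesions.

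**Overall response.** Section 9.4 states: "Best overall response is the best response recorded from the start of radiation therapy until disease progression or recurrence". In its table, with no new lesion, row 1 maps target CR and non-target CR to overall CR. Row 2 maps target CR and non-target PR or SD to overall PR. Row 6 maps non-target PD to overall PD whatever the targets do.

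**Nodes.** Section 9.2 says: "A lymph node will be considered measurable if it measures at least 15 mm in short axis". It then chooses target lesions by longest diameter and continues: "A sum of the longest diameters for all target lesions will be calculated and reported as the baseline sum diameters". It makes no exception for nodes.

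**Use of the sum.** Local Progressive Disease in 9.3 needs a rise in the target sum of at least 20% and at least 5 mm. Section 13.3 says that 1-year local control will be assessed by RECIST 1.1, the guideline also named in 9.1.

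**The concern.** The two defects are independent, with different causes and different consequences.

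The first lets one set of scans carry two overall responses. The persisting lesion may be one that was irradiated. Section 5.1 allows up to 10 treated lesions and sets a maximum size but no minimum. Section 9.2 caps targets at five, two per organ, and treats lesions under 10 mm, or nodes under 15 mm in short axis, as non-measurable. Some treated lesions will therefore be non-target, and a literal reading allows an overall CR while treated disease remains.

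The second concerns which measurement decides nodal progression. Abdominal/pelvic nodes are one of six eligible sites. A node is selected on one axis and followed on another, and the two axes can disagree about the progression threshold. The sum feeds Local Progressive Disease, so the disagreement can reach 1-year local control.

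**Working it through.** The plan gives no figure for this point, so there is none to reproduce. The check applies the written rules to fixed scenarios.

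**1. Non-target CR.** Inputs: the 9.3 definitions and the 9.4 table. In every row below, all targets have gone and there is no new lesion.

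| Non-target lesions | Non-target categories met as written | Overall response from 9.4 |
|---|---|---|
| All gone | CR | CR |
| At least one persists, no progression | CR (targets gone) and SD (lesion persists) | CR by row 1, PR by row 2 |
| At least one unequivocally progresses | CR, SD and PD | CR by row 1, PR by row 2, PD by row 6 |

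The second row is the main conflict. In the third, row 6 is written to apply to any target response and can reasonably be taken to prevail, but the literal CR entry still competes with it.

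The opposite case leaves a gap. If every non-target lesion goes while a target remains, CR is not met (a target is present), SD is not met (no non-target lesion persists) and PD is not met. The overall response is still determined, because rows 3 and 4 ask only that the non-target lesions have not progressed.

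If non-target CR is defined by the non-target lesions, the second row gives SD and hence PR only. In the third, CR is no longer reachable and row 6 gives PD.

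**2. Nodal axis.** Inputs: the 9.3 thresholds (20% and 5 mm, both required) and assumed sizes, short axis by longest diameter, for a patient whose only target is one node. Change is (follow-up − baseline) / baseline. Baseline is taken as the smallest sum on study, so the choice of reference in 9.3 does not matter here.

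| Node, mm | Short axis | Longest diameter |
|---|---|---|
| 15x30 to 21x33 | (21−15)/15 = +40%, +6 mm: progression | (33−30)/30 = +10%, +3 mm: none |
| 20x30 to 26x34 | (26−20)/20 = +30%, +6 mm: progression | (34−30)/30 = +13%, +4 mm: none |
| 16x20 to 17x26 | (17−16)/16 = +6%, +1 mm: none | (26−20)/20 = +30%, +6 mm: progression |

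The first two nodes progress only on short axis and the third only on longest diameter, so the mismatch works both ways.

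**Dilution by other targets.** A 6 mm rise reaches 20% only if the baseline sum is at most 6/0.20 = 30 mm. With other targets unchanged, the disagreement in the first example survives only if they contribute no more than 30 − 15 = 15 mm. In the second and third examples the limit is 30 − 20 = 10 mm.

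**3. Reach.** The criteria in 13.4 for advancing to a later trial use toxicity and feasibility only. Their stated probabilities reproduce at n=30: P(X≤4) is 0.798 at a toxicity rate of 10.5% and 0.200 at 21.4%; P(X≥24) is 0.802 at a feasibility rate of 83.9% and 0.200 at 71.3%. None depends on response.

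**The case against.** **The CR entry is an obvious slip.** It stands under a heading about non-target lesions, next to an SD entry that names them. On the literal reading target CR would always imply non-target CR, which would leave row 2 of the table with no work of its own. An assessor applying RECIST 1.1 would be unlikely to record CR with a lesion still visible. This stands as an argument about likely practice, and it makes the intended meaning clear. It does not make the written rule right. Sections 9.2 to 9.4 set out their own rules, including a split into local and distant progression, and do not say whether they or the named guideline governs when up to five sites score scans.

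**Best overall response is not an objective.** That is correct. The undefined non-target PR is also harmless in practice, since PR/SD can only operate as SD.

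**Nothing in the documents says nodes must be followed on short axis.** Also correct: this is a mismatch between qualifying and following, not a flat contradiction. The documents contain no nodal rule for CR either, so none is relied on here.

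**The link to local control is inferred.** Section 13.3 names RECIST 1.1 without defining the event or citing the 9.2 sum. Local Progressive Disease is the only local-progression rule written in the plan, so the link is reasonable, but it is not stated.

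A reader might infer that nodal progression will be systematically missed and local control overstated. The documents do not support that: the third node above shows the opposite error, and no data on node shape or frequency are given.

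**Conclusion.** Both defects are real and should be corrected, but their reach is limited.

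- **Non-target CR:** as written, any patient with all targets gone, a persisting non-target lesion and no new lesion can be scored both CR and PR. This affects response reporting only. A reader might infer that it distorts local control or the decision to advance; it does not, because the non-target progression rule is intact and that decision does not use response.
- **Nodal axis:** progression can be missed or falsely called for 1-year local control. This is confined to nodes of at least 15 mm in short axis that are chosen as targets, and it matters most where other targets add little to the sum. Direction and frequency are unknown. The conclusion assumes that local control is scored through Local Progressive Disease, and the examples rest on assumed sizes for a single target node.

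The primary feasibility and tolerability criteria and the n=30 operating characteristics are unaffected.

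**What to change.** 1. In 9.3, define non-target CR as the disappearance of every non-target lesion.
2. In row 2 of the 9.4 table, replace PR/SD with the category that 9.3 defines, incomplete response/SD.
3. In 9.2, state that nodal targets enter the sum by short axis, the axis on which they qualify, at baseline and at every follow-up.
4. Reconcile 9.2 to 9.4 with the RECIST 1.1 standard named in 9.1 and 13.3, and say which governs if they differ.

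The first two are wording changes with no effect on data collection. The third has a cost: for any nodal target whose baseline is already recorded, the short axis must be read again from existing scans, and likewise at any follow-up where only the longest diameter was recorded. No change to sample size or to the primary analysis is needed.

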#### 13.3 Secondary objectives

1-year local control (LC) will be assessed according to RECIST 1.1 criteria and will be estimated using the Kaplan-Meier method along with the corresponding 95% confidence interval from the time of study treatment

1-year overall survival (OS) will be estimated using the Kaplan-Meier method along with the corresponding 95% confidence interval from the time of study treatment

The proportion of patients who experience acute grade 3 or higher toxicity attributable to SABR will be determined along with the corresponding 95% confidence interval. For patients receiving SABR to multiple lesions, acute toxicity will be determined from the date of the initiation of SABR.

Patient-reported quality of life will be determined using the FACT-G survey instrument prior to and after SABR.

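### The local-progression rule in section 9.3 gives one percentage increase two reference sums, so the same regrowth after shrinkage can be scored as local failure or as local control

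*Combined protocol and SAP*

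**What the plan says.** In section 9.3, LPD requires a relative rise of at least 20% in the target-lesion sum and an absolute rise of at least 5 mm. The relative rise is stated as "compared to baseline sum of target lesions, taking as reference the smallest sum on study". A parenthesis adds that baseline counts as the smallest sum when it is the smallest. Stable disease (SD), in the same list, is judged "taking as reference the smallest sum diameters while on study". Section 9.2 gives the baseline sum a different job, as the reference for regression.

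Section 9.4, on best overall response, words the progression reference as "taking as reference for progressive disease the smallest measurements recorded since SABR".

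In the non-target block of section 9.3, complete response (CR) is defined as "Disappearance of all target lesions", the same words as the target-lesion definition above it. SD in that block is the persistence of at least one non-target lesion.

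Section 13.3 states that "1-year local control (LC) will be assessed according to RECIST 1.1 criteria" and estimated by Kaplan-Meier with a 95% confidence interval. It does not name LPD as the event and does not give a reference sum.

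**The concern.** A percentage increase needs one denominator, and the LPD sentence supplies two. They are equal only while no earlier sum has fallen below baseline. In a patient whose lesions have shrunk, a reader using baseline will not call a moderate regrowth, and a reader using the lowest sum will.

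LPD is the only rule in section 9 labelled as local progression, and 1-year local control is a secondary objective. Up to five sites take part. Section 8.3 has a delegated study team member perform the RECIST evaluation, and the documents describe no central imaging review. Both the number and the dates of local failures could therefore depend on which half of the sentence a reader follows.

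The wording in 9.4 and the non-target CR line raise the same kind of problem for overall response: one set of scans can receive two classifications.

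**Working it through.** The plan states no figure for local control, so there is none to reproduce. The check applies the plan's own thresholds to illustrative sums. The sums are assumptions; 40 mm and 30 mm are possible for a single lesion under the 5 cm limit in section 5.1.

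**LPD threshold.** For a reference sum R, LPD is called once the current sum reaches the larger of 1.2 × R and R + 5 mm. The 20% limit governs when R is 25 mm or more (5 / 0.20 = 25).

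**Case 1: baseline 40 mm, then 20 mm, then 30 mm.**
- Against the smallest sum on study: 30/20 - 1 = +50%, +10 mm. LPD.
- Against baseline: 30/40 - 1 = -25%. Not LPD.

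**Where each reading starts to call LPD, baseline 40 mm.**

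| Lowest sum | From lowest sum | From baseline |
|---|---|---|
| 20 mm (halved) | max(24, 25) = 25 mm | max(48, 45) = 48 mm |
| 28 mm (30% decrease, the limit for partial response) | max(33.6, 33) = 33.6 mm | 48 mm |

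After halving, the required regrowth is 25/20 - 1 = 25% under one reading and 48/20 - 1 = 140% under the other. Any sum from 25 mm to just under 48 mm is classified differently.

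**Direction.** The smallest sum on study is never larger than baseline, so its LPD threshold is never higher. Every LPD against baseline is also an LPD against the smallest sum on study. The reverse fails only after shrinkage. Enlargement alone never separates these two readings.

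**Size of one changed call.** With 30 patients and censoring ignored, one reclassified patient moves a simple local-control proportion by 1/30 = 3.3 percentage points.

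**Section 9.4 wording, for best overall response: baseline 30 mm, then 34 mm, then 37 mm.**
- Against baseline, which is also the smallest sum on study: 37/30 - 1 = +23.3%, +7 mm. The progression limits are met.
- Against the smallest since SABR, read literally as excluding baseline: 37/34 - 1 = +8.8%, +3 mm. Not met.

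These two references differ only if every earlier post-SABR sum exceeds baseline. If any earlier post-SABR sum is at or below baseline, they coincide.

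**Non-target CR.** Take a patient whose target lesions have all disappeared, with a non-target lesion persisting and no new lesions. Read literally, the non-target status is CR (the target lesions are gone) and also SD (a non-target lesion persists). The table in 9.4 then gives overall CR from its first row and overall partial response from its second.

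**The case against.** The strongest reply is that the intended reference is clear. The parenthesis about baseline has a purpose only if the reference is the smallest sum. The SD definition uses that reference too, and section 9.2 assigns baseline to regression. On this view the baseline phrase is a leftover. This stands as evidence of intent and decides which way to correct the text. It does not remove the phrase, which is still operative in the only local-progression rule.

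A reader might infer that the local-progression rule carries three competing references. It does not. The LPD sentence names two, and the since-SABR wording belongs to best overall response, which is neither a listed secondary objective nor a planned analysis in 13.3. The 30, 34, 37 mm example therefore does not bear directly on the local-control estimate.

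A reader might also infer that the references agree only if lesions never change size, or that most patients would be affected. Neither is supported. A sum that is unchanged at the first scan and enlarges later has the same reference under all three wordings. For baseline and smallest-on-study to give different calls, a shrunken sum must regrow by the stated amounts and still stay under the baseline threshold. The documents give no response or regrowth rate from which to estimate how often that happens.

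The non-target CR line is evidently a copying slip, since the second row of the 9.4 table would serve no purpose under the literal definition. It does not affect local control.

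**Conclusion.** Wrong as written; minor. The LPD definition contradicts itself, and for a sum that shrinks and then regrows the two readings can give opposite calls. For a sum halved from 40 mm, the disputed range runs from 25 mm to just under 48 mm. This can change event counts and dates in the 1-year local-control estimate. How often is unknown; the examples show that it can happen, not how frequently.

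The size of the effect also rests on whether any reader would follow the baseline phrase, which the documents do not show. If all readers use the smallest sum on study, the local-control result is the same.

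It would be too strong to infer that the trial's main conclusions are at risk. Local control is a descriptive secondary estimate. The primary criteria (13.2), the closure rule (11.5) and the criteria for advancing to a later-phase trial (13.4) use only toxicity and feasibility. The 9.4 wording and the non-target CR line are separate errors confined to response classification.

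**What to change.** Make four wording edits:

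1. In 9.3, delete the LPD phrase that compares with the baseline sum. Keep the smallest sum on study, with the parenthesis that includes baseline.
2. In 9.4, replace the since-SABR reference with the same wording.
3. In the non-target block of 9.3, define CR as the disappearance of all non-target lesions.
4. In 13.3, cite the corrected LPD rule as the reference for local control.

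No new scans or data are needed. The downside is that reported local control may be slightly less favourable if any reader would otherwise have used baseline, because some regrowths would be called that were not called before, or called earlier. The edits are best made before local-control results are examined, so that the reference is not chosen with the outcomes in view.

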### 1.2 Single-fraction SABR

While SABR is delivered in as few as 1 but up to 5 daily fractions by definition, the vast majority of published outcomes data have used 3-5 fractions. Nonetheless, there are published prospective and retrospective studies for single-fraction SABR as summarized in a recently published critical review by Ng and colleagues(10). The most substantial supporting data for single-fraction SABR exists for early-stage peripheral non-small lung cancer (NSCLC) for which several randomized trials have been completed showing no significant difference in outcomes between single- and multi-

fraction regimens(11,12). Despite these randomized data, the utilization of single-fraction SABR for early-stage NSCLC has been scarce. Safety and feasibility of single-fraction SABR has been demonstrated for other anatomic sites including the liver (13), lymph nodes (14), adrenal gland(15), and the kidney(16). Single-fraction SABR for locally advanced pancreas cancer has been prospectively evaluated (notably without intrafraction image guidance or daily adaptive replanning), and has been associated with increased gastrointestinal toxicity compared to fractionated SABR(17).

A single-fraction regimen should be at least isotoxic and isoeffective as compared to multi-fraction SABR for such an approach to be considered a reasonable alternative. Assuming that both are true, then there are several advantages of completing treatment in one fraction including reduced cost(18), potentially reduced lymphopenia(19), and increased patient convenience. One reason that clinicians may be hesitant to use single-fraction SBRT is concern about geographic miss, which stems from the lack of intrafraction evaluation of the tumor and internal anatomy using a linear accelerator using x-ray and/or CT-guidance(20). Furthermore, generous margins may be placed on the gross tumor to decrease the risk of a geographic miss, thereby increasing normal organ dose and potentially increasing the risk of more severe toxicity(21).

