### 5. PATIENT SELECTION

#### 5.1 Inclusion criteria

1.  $\geq 18$  years of age at the time of study enrollment
2. Biopsy-confirmed primary or metastatic carcinoma with involvement of the lung, liver, adrenal gland, pancreas, kidney, and/or abdominal/pelvic lymph node that would receive SABR
3. Any lesion that would receive SABR is no larger than 5 cm in greatest dimension
4. 1-10 total lesions that would receive SABR
5. If multiple lesions are treated, they must be at least 3 cm apart
6. Eastern Cooperative Oncology Group (ECOG) performance status of 0-2
7. Life expectancy at least 6 months
8. Women of childbearing potential and men must agree to use adequate contraception (hormonal or barrier method of birth control) prior to study entry and for the duration of study participation. Abstinence is acceptable if preferred by patient. Should a woman become pregnant or suspect she is pregnant while participating in this study, she must inform her treating physician immediately.

9. Patients receiving hormonal therapy or immunotherapy such as immune checkpoint inhibitor that had begun at least 4 weeks prior to SABR will be allowed.

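### Section 9.3 labels a new lesion distant wherever it lies and section 13.3 names no local control event, so a separate new nodule in a treated volume may drop out of 1-year local control

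*Combined protocol and SAP*

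**What the plan says.** Section 9.3 defines response separately for target and non-target lesions.

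- **Target block, local progression (LPD):** "At least a 20% increase in the sum of the diameters of target lesions compared to baseline sum of target lesions", referenced to the smallest sum on study and with an absolute rise of at least 5 mm.
- **Target block, distant progression (DPD):** "The appearance of at least 1 new lesion". Nothing is said about where the lesion lies relative to the GTV, the PTV or the treated organ.
- **Non-target block:** progression is "Appearance of one or more new lesions and/or unequivocal progression of existing non-target lesions", labelled PD without a local or distant qualifier.

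The overall response table in section 9.4 uses only PD.

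Section 9.2 fixes the target lesions at baseline: "Target lesions include measurable lesions up to a maximum of two lesions per organ and up to five lesions in total". They are chosen by size and reproducibility of measurement.

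For the endpoint, section 13.3 states that "1-year local control (LC) will be assessed according to RECIST 1.1 criteria", with a Kaplan-Meier estimate and 95% confidence interval. The Statistical Methods part of the Protocol Summary says the same. Neither place says which category in section 9.3 is the event. No section defines in-field, marginal or out-of-field failure.

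**The concern.** Local control after SABR should describe what happens at the irradiated site. Section 9.1 points that way, since it asks for contrast where it is needed to see the treated lesion and judge local response. Section 9.3 nevertheless sorts local from distant by whether the lesion was in the baseline sum, and location plays no part.

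A discrete nodule that appears later inside a treated PTV, or touching it, was not in the baseline sum and cannot raise it. The target block therefore labels it distant. If the Kaplan-Meier event is LPD, that patient stays locally controlled in the analysis, and the resulting error can only raise the estimate. If the event is instead any RECIST progression, the nodule is counted, but so is every new lesion far from the treated volume. The plan does not say which of these applies, and neither measures control of the treated site.

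**Working it through.** The documents give no expected local control rate, event count or precision target, so there is no stated figure to reproduce. The check has two parts.

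**1. Applying the section 9.3 rule to hypothetical measurements**

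The LPD rule is: current sum − smallest sum ≥ 5 mm, and (current sum − smallest sum) / smallest sum ≥ 20%. The relative condition is taken as met when the smallest sum is zero.

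| Case | Smallest sum → current sum | Change | Label in target block |
|---|---|---|---|
| Single target, complete response, then regrowth in place | 0 → 8 mm | +8 mm | LPD |
| Single target enlarging | 20 → 26 mm | +6 mm, 6/20 = +30% | LPD |
| Single target stable, separate new 10 mm nodule at the PTV edge | 20 → 20 mm | 0 mm, 0% | not LPD; DPD |

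Regrowth of an irradiated target lesion is caught once it passes the thresholds, even after complete response. Only the separate new nodule goes to the distant category.

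**2. What one relabelled patient does to the estimate**

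Assumptions, none of which the documents supply except n = 30 (section 13.4): the patient is the unit, there is no censoring, LPD is the event, k patients have a true local failure, and in m of these the failure is a separate nodule labelled distant. With no censoring, the Kaplan-Meier estimate at 1 year is a simple proportion:

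reported local control = 1 − (k − m)/30

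Each relabelled patient adds 1/30 = 3.3 percentage points. Exact (Clopper-Pearson) 95% limits are in the last column.

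| k | m | Reported local control | 95% CI |
|---|---|---|---|
| 3 | 0 | 27/30 = 90.0% | 73.5–97.9 |
| 3 | 1 | 28/30 = 93.3% | 77.9–99.2 |
| 5 | 0 | 25/30 = 83.3% | 65.3–94.4 |
| 5 | 1 | 26/30 = 86.7% | 69.3–96.2 |
| 5 | 2 | 27/30 = 90.0% | 73.5–97.9 |
| 5 | 3 | 28/30 = 93.3% | 77.9–99.2 |

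The rows with m = 0 are the correct values for that k. Every shift shown lies inside the confidence interval of the m = 0 row.

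**The case against.** There is a good case that this is a narrow problem.

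- **Most recurrence at the site may be read as growth of the treated lesion.** The PTV extends only 3 mm (preferred) or 5 mm beyond the GTV/CTV (section 6.4.3), so tumour reappearing there may often merge with the original lesion and enter the sum. This stands. The documents do not show how often a discrete nodule would be seen instead.
- **New lesions are not uniformly called distant.** The non-target block and the section 9.4 table say only PD. This also stands, but it does not rescue the event: PD without a qualifier is not labelled local either, and one section then gives the same finding two labels.
- **Section 13.3 does not make LPD the event.** This is correct, so the bias is conditional. The silence is itself part of what needs repair.
- **Little depends on it.** Local control is secondary, carries no threshold, and is absent from the three advancement criteria in section 13.4. This stands and limits the severity.

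A reader might infer more from section 1.2, which says "One reason that clinicians may be hesitant to use single-fraction SBRT is concern about geographic miss", and conclude that the DPD rule hides exactly the failure a geographic miss would produce. The documents do not support that step. Section 1.2 links the miss to lack of intrafraction evaluation of the tumour. The under-dosed tissue would then be the lesion present at baseline, and its growth enters the LPD sum if it is a target lesion. Nothing says that a miss shows itself as a separate nodule.

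**Conclusion.** The point holds in a limited form. Section 9.3 applies a stated rule that labels a separate new nodule inside or touching a treated PTV as distant, and section 13.3 does not define the local control event. If LPD is that event, which is the natural reading because no other category is labelled local, 1-year local control is biased upward.

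The documents do not allow the bias to be sized. The 3.3 points per patient rests on 30 patients, the patient as the unit and no censoring, and the failure counts are assumed. An example such as 93.3% instead of 90.0% is within sampling error.

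Two stronger conclusions might be drawn and should not be. One is that recurrence in an irradiated volume never counts; regrowth of a treated target lesion does count once it meets the LPD thresholds. The other is that local control will certainly be overstated; that depends on an event definition the plan does not give and on failures that may be few. This is a modest correction to a secondary endpoint.

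**What to change.** **Section 9.3.** Limit DPD to new lesions lying wholly outside the PTV of every lesion treated on study. Add to the local definition a new lesion within or touching such a PTV. Make the new-lesion wording in the non-target block refer to the same rule, so that one event has one label.

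**Reference volume.** State that the comparison uses the full PTV and not the PTVopt of section 6.7, on the plan actually delivered: the adapted plan if adaptation was done, otherwise the original. Section 6.9 stores both, so the text must say which governs. Using the full PTV also settles how to class a new lesion where the PTV overlaps the expanded gastrointestinal structures, since section 6.7 sets no minimum coverage there.

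**Section 13.3 and the matching summary text.** State that the local control event is local progression as redefined in 9.3, and that DPD alone is not an event.

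Overall PD in section 9.4 is unchanged, and the change concerns endpoint classification only. A nodule just beyond the PTV would still be distant; if the sponsor prefers a wider zone, it should be fixed before the data are read.

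**Cost.** These are wording changes, plus a comparison with the stored plan when a new lesion appears near a treated site. Reported local control may be slightly lower.
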